14.4 Secondary Effectiveness Variable

The secondary effectiveness variables for this study are:

- PVR through the first removal visit is ≤ 150 ml of urine (Visits 1 and 2)
- PVR through the first removal visit is ≤ 250 ml of urine (Visits 1 and 2)
- PVR through the third removal visit is ≤ 250 ml of urine (Visits 1-4)

14.5 Exploratory Effectiveness Variable

The exploratory effectiveness variables for this study are:

- Qmax measurement
- IPSS Total Symptom Score

Qmax measurements will be taken from the initial stent placement forward (Visits 1, 2, 3 and 4), while the IPSS instrument will be administered from the initial stent removal forward (Visits 2, 3, and 4). Qmax and IPSS scores will be the change from baseline values (Visit 1 for Qmax and Visit 2 for IPSS).

14.6 Safety Variables

Safety variables that will be recorded are:

- Treatment emergent adverse events deemed to be related to the implantation procedure

CONFIDENTIAL

- Treatment emergent adverse events deemed to be related to the device
- All other adverse events

14.6.1 Analysis Populations

The following analysis populations will be defined.

- Intent-to-Treat (ITT) Population – The ITT population will consist of any enrolled subject who underwent an attempted Spanner device implant procedure.
- Per Protocol (PP) Population – The PP population will consist of all subjects who are enrolled in the study, have been implanted with a Spanner device, and have completed all study visits with no major protocol deviations while enrolled in the study².
- Safety Population – The safety population will consist of all subjects who are enrolled in the study.

The analysis of the primary and secondary efficacy endpoints will be conducted on ITT and PP populations. The primary analysis set will be the ITT analysis. All safety analyses will be conducted on the safety population.

The study subjects to be excluded from the PP analysis set and the reasons for their exclusion will be determined and documented prior to statistical analysis. These decisions will not be outcome-data driven.

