9.3.1.2 Post Void Residual Urine (PVR) Testing

PVR will be determined using abdominal ultrasound:

- Subjects with a minimum PVR > 350 ml will be prematurely removed from the study (see Section 21.5.8).
- Subjects with a minimum PVR greater than 250 ml (and less than 350 ml) will be scheduled for a follow-up visit within one week to monitor PVR.

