14.3 Primary Effectiveness Variable and Pass/Fail Criteria

The primary effectiveness endpoint is the success/failure of the subject to have a successful urinary void at all four study visits: (a) upon initial placement of the first stent (Visit 1), and (b) at all three visits in which the subject has a stent placed for 30 days (Visits 2, 3 and 4).

The primary effectiveness endpoint will be marked as a failure for a subject if any of the following occur:

- PVR of >150 ml at any visit (Visits 1, 2, 3, and 4)
- The subject withdraws from the trial

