21.5.7 Occlusion of the Device Drainage Lumen or Device Malfunction

If occlusion or malfunction of the device is suspected, The Spanner should be removed. A Device Deficiency eCRF should be completed and the device returned to the Sponsor. The subject should continue in the study and attend the next study visit.

21.5.8 Criteria for Spanner Removal and Re-establishment of Bladder Drainage: Clinically Significant Post Void Residual Urine

For purposes of the clinical trial, PVR > 350 ml on two measurements taken within a few hours will be considered as significant and requiring intervention. If the subject has a PVR > 350 ml on two measurements taken within a few hours at any scheduled or visit, or at other medical visit, the intervention should include the removal of The Spanner, the re-establishment of bladder drainage (CIC or Foley) and the premature withdrawal of the subject from the study.

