ATTACHMENT B: SPANNER STUDY PROCEDURE FOR UROFLOW TESTING

REQUIREMENT FOR A VALID UROFLOW TEST

Enrollment Period – Visits 1, 2, 3 and 4:

Once the participant is consented in the study they will have two attempts within a few hours to obtain PVR of 150 ml or less.

Subjects will be withdrawn from the study only if they have a PVR of 350 ml or more on both attempts.

TEST ENVIRONMENT

The test should be conducted in a quiet, non-rushed environment in a location that provides for subject comfort and privacy.

EQUIPMENT SET UP

Prior to testing, verify correct operation and maintenance of the uroflowmeter. Complete any calibration or equipment set up recommended by the equipment manufacturer.

ORIENTATION OF THE SUBJECT TO UROFLOW TESTING

To reduce the influence of the test equipment and test environment on subject performance during testing, subjects participating in the study should be given an orientation prior to their first uroflow test under the study protocol.

The orientation should consist of instruction on how to void into the test equipment and a simulated use demonstration (i.e. pouring water into the test set up) to show the subject how to do the test and how the equipment operates (e.g. if any operation of the equipment, like printing, occurs during testing). Any instructions or precautions related to the specific uroflow equipment that will help achieve a technically good test should be reviewed with the subject.

SUBJECT TESTING

- Have the subject drink two to four 8 oz. glasses of water.

Hand out the *How to Perform a Voiding Test* Sheet to the subject, asking him to review it prior to testing. Copies for distribution to study participants are provided in the individual case report form notebooks. (See sample on following page.)

- Instruct him to return for testing when he has a full bladder and strong urge to void.

CONFIDENTIAL

RECORDING THE TEST RESULT

Record the values from the uroflow printout where indicated on the eCRF. In addition, due to the limitations of the uroflow equipment to account for artifacts, the investigator's manual reading of the uroflow graph is optional based on investigator discretion. Record the investigator reading on the eCRF with the corresponding machine values, which must include Qmax in ml/s. Label the report with the test date, subject initials and ID number. Place the uroflow test reports and graphs in the subject notebook.

~~~~~

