7. ANALYSIS POPULATIONS

The following populations will be considered for the summarization and analysis of the data from this study:

Intention to Treat Population

The Intention to Treat (ITT) population includes The ITT population will consist of any enrolled patient who underwent an attempted Spanner device implant procedure. This population will be used for all of the analyses unless otherwise stated.

Per Protocol Population

The Per Protocol (PP) population will consist of all patients who are enrolled in the study, have been implanted with a Spanner device, and have completed all study visits with no major protocol deviations while enrolled in the study. A major protocol deviation is defined as any protocol deviation that may affect the primary endpoint. The PP population will only be used as an analysis population if the ITT population produces unexpected results that could have been caused by protocol deviations.

Safety Population

The safety population will consist of all subjects who are enrolled in the study.

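### The per-protocol set requires completion of all visits, yet the protocol withdraws men for very high PVR, so it drops primary failures because they failed

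*Protocol*

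**What the plan says.** - **PP membership.** Protocol 14.6.1 admits enrolled, implanted men who "have completed all study visits with no major protocol deviations while enrolled in the study". SAP 7 repeats the condition: "have completed all study visits with no major protocol deviations".
- **Safeguard.** Of PP exclusions, Protocol 14.6.1 says: "These decisions will not be outcome-data driven".
- **Withdrawal for PVR.** Protocol 9.3.1.2: "Subjects with a minimum PVR > 350 ml will be prematurely removed from the study". Protocol 21.5.8, for PVR above 350 ml on two measurements a few hours apart, calls for stent removal, "the re-establishment of bladder drainage (CIC or Foley) and the premature withdrawal of the subject from the study". Attachment B: "Subjects will be withdrawn from the study only if they have a PVR of 350 ml or more on both attempts".
- **Primary failure.** Protocol 14.3 lists PVR above 150 ml at any of Visits 1 to 4, and also "The subject withdraws from the trial". SAP 4.2.1 adds failure to attend any of the four visits.
- **Use of PP.** Protocol 14.6.1 plans the primary and secondary efficacy analyses on both ITT and PP, with ITT as the primary set. SAP 7 restricts PP to the case where ITT gives unexpected results that protocol deviations could explain.

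**The concern.** A per-protocol set is meant to remove men who departed from the protocol. A man withdrawn at Visit 1, 2 or 3 under the protocol's own PVR rule has not departed from it. He is among the clearest failures the study can produce, and the completion condition still takes him out of the denominator. A man who drains well completes the visits and stays in.

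Completion is therefore part of the outcome, and the safeguard in 14.6.1 cannot hold as written. Documenting exclusions before analysis does not help, because the selection is built into the definition. In a single-arm trial judged against a fixed 50%, no control arm offsets the shift. At stake is a reported PP rate that looks better than the device's performance and could be read as support when ITT falls short.

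**Working it through.** **Membership.** Take a man whose PVR exceeds 350 ml on both measurements at Visit 2.

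1. Protocol 21.5.8 withdraws him.
2. Under Protocol 14.3 he fails twice: PVR above 150 ml, and withdrawal.
3. He has no Visit 3 or 4, so he has not completed all visits and is outside PP.

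More generally, Protocol 14.3 and SAP 4.2.1 make any withdrawal or missed visit among Visits 1 to 4 a primary failure. Every man excluded from PP for missing one of those visits is then an ITT failure, and no ITT success is lost that way. This relies on those endpoint definitions; Protocol 14.11 (multiple imputation) and SAP 8 (observed data first) treat missing outcomes differently. A man whose high PVR was recorded at a study visit is an observed failure under any of these rules.

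**Inputs.** N = 105, the null rate of 50% and the exact binomial test are in Protocol 14.1, 14.2 and 14.6.3 and in SAP 5.3. The plan gives no PP rate and no PVR-withdrawal rate, so there is no planned figure to reproduce here. The number withdrawn is my assumption.

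**Fixed example.** Let S be ITT successes and W the failures removed. The PP rate is S/(105 − W), and p is the exact upper binomial tail at 0.5. Take S = 58, so 105 − 58 = 47 men failed.

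| W (assumed) | PP result | Rate | One-sided p | Successes needed at 0.025 / 0.05 |
|---|---|---|---|---|
| 0 (= ITT) | 58/105 | 55.2% | 0.165 | 64 / 62 |
| 5 | 58/100 | 58.0% | 0.067 | 61 / 59 |
| 10 | 58/95 | 61.1% | 0.020 | 58 / 57 |
| 20 | 58/85 | 68.2% | 0.0005 | 53 / 51 |

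Both one-sided levels are shown because Protocol 14.6.3 tests at 0.025 and SAP 13.2 uses a one-sided 95% bound. ITT fails at either level. PP fails with 5 removed and passes at both levels with 10 or 20 removed.

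**Expected shift.** If the ITT success rate is p and a share w of men is withdrawn for PVR, the PP rate is p/(1 − w). At p = 50% this gives 0.50/0.95 = 52.6%, 0.50/0.90 = 55.6%, 0.50/0.85 = 58.8% and 0.50/0.80 = 62.5%.

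Now let the number withdrawn be binomial(105, w) and apply the exact test at one-sided 0.025 to the men who remain. The chance that PP rejects when the true ITT rate is exactly 50% is:

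| w (assumed) | 0 | 5% | 10% | 15% | 20% |
|---|---|---|---|---|---|
| PP rejects | 1.6% | 6.3% | 16.4% | 34.7% | 59.2% |

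**The case against.** **The deciding analysis is ITT.** This stands. Withdrawals count as failures there under Protocol 14.3 and SAP 4.2.1, the primary results table in SAP 13.2 is specified for ITT, and no success criterion is attached to PP. A reader might infer that the PP definition could turn a failed trial into a successful one; under the stated rule it cannot.

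**The SAP trigger is conditional.** A reader might infer that SAP 7 turns to PP whenever ITT disappoints. It requires that protocol deviations could explain the result, and a withdrawal the protocol itself calls for is not a deviation. But Protocol 14.6.1 plans PP alongside ITT without that condition.

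**Most device events do not mean withdrawal.** A reader might extend the point to all men with pain, bleeding or infection. Sections 21.5 to 21.5.7 mostly keep such men in the study, even after stent removal, so they can complete the visits and stay in PP. Only those who actually withdraw are lost.

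**The 20% dropout figure.** A reader might cite it in support of 10 to 20 removals. SAP 5.3 defines dropouts as exits without a PVR failure, so it excludes this group. Those exits are a separate route out of PP. Twenty percent of 105 is 21, and removing 21 such men with no PVR withdrawals turns 52/105 (49.5%, p=0.58) into 52/84 (61.9%, p=0.019).

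**The bias need not be upward overall.** Correct. A major deviation can exclude a success, and so can a missed follow-up call if it counts as a study visit (Protocol 12.1.7 calls it a telephone visit). For the 30-day secondary endpoints, a man who met the criterion at Visits 1 and 2 and was withdrawn at Visit 3 would be a success lost. The one-way argument covers only the primary endpoint and Visits 1 to 4.

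**Some failures stay.** Men at 151 to 350 ml who attend every visit remain in PP as failures. A man first above 350 ml at Visit 4 has attended every clinic visit.

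**The wording could be read leniently.** The closing words of "have completed all study visits with no major protocol deviations while enrolled in the study" might mean visits up to withdrawal, which would keep these men. They more naturally qualify the deviations. If the lenient reading is meant, the text should say so.

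**Conclusion.** The point holds as a defect in a planned, non-primary analysis. On the natural reading, the completion condition removes men withdrawn for PVR before Visit 4, who kept to the protocol and failed the endpoint. Through Visits 1 to 4 it can remove only primary failures, so on that route the PP rate for the primary endpoint is biased upward, contrary to the safeguard in 14.6.1. The direction rests on the failure rules in Protocol 14.3 and SAP 4.2.1.

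The size rests on a withdrawal count the documents do not give. For 58 ITT successes, 5 to 20 removals move the rate from 55.2% to between 58.0% and 68.2%. The documents do not support the further inferences that the trial's formal conclusion is at risk, that the total PP bias must be upward, or that the planned dropout rate shows how large it is.

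**What to change.** In Protocol 14.6.1 and SAP 7, replace "have completed all study visits with no major protocol deviations while enrolled in the study" with: *have no major protocol deviations while enrolled and have completed all visits up to Visit 4 or up to the first primary-endpoint failure (PVR >150 ml or withdrawal from the study), whichever comes first*.

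- State that these men stay in PP as failures.
- Do not make membership depend on whether an adverse event is judged device-related; in an open-label study that would bring judgement back into the selection.
- State that the follow-up call is not required for PP.
- A man who skips a visit but stays in the study, with no earlier failure, would still leave PP. The text should say that this is intended.
- Reconcile the PVR withdrawal wordings in Protocol 9.3.1.2 (a minimum above 350 ml), 21.5.8 (above 350 ml on two measurements) and Attachment B (350 ml or more on both attempts), and the description of the 21.5 rules as guidelines, so that the withdrawal event is unambiguous.
- Align the protocol and SAP on when PP is analysed.

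The PP definition costs one sentence in each document, needs no new data and changes no clinical rule. The downside for the sponsor is a less favourable PP rate.

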14.6.2 Analysis of Baseline and Demographic Characteristics

Baseline and demographic characteristics will be summarized for all subjects in the safety population. Continuous variables will be displayed via summary statistics (mean, median, sample size, standard deviation, minimum, and maximum). Categorical variables will be summarized via counts and percentages.

14.6.3 Analysis of the Primary Effectiveness Variable

The following hypotheses will be tested at a one-sided $\alpha=0.025$ level of significance:

$$H_{a0}: p_s \leq 50\% \quad \text{vs.} \quad H_{a1}: p_s > 50\%$$

where p_s is the proportion of subjects with maintenance of successful voiding during the Spanner implantation period. This hypothesis will be tested using a one-sample exact binomial test. Summary statistics (counts and percentages) will be computed on the primary endpoint along with a 95% confidence interval on the treatment group success proportion.

² A major protocol deviation is defined as any protocol deviation that may affect the primary endpoint.

14.7 Analysis of the Secondary Effectiveness Variables

The statistical analysis of the secondary effectiveness variables will be described in the Statistical Analysis Plan (SAP) document for the study. The SAP will be completed and signed by the Sponsor before the enrollment of the first subject in the study.

14.8 Analysis of Safety Variables

All adverse events (AEs) will be observed for each subject from enrollment until termination from the study. A treatment emergent adverse event is defined as an adverse event whose start date is on or after the procedure date. If the procedure date and/or the AE start date are missing, the AE will be considered treatment emergent.

Prior to analysis, all adverse events (AEs) will be coded using the Common Terminology Criteria for Adverse Events (CTCAE). All AEs will be listed.

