7.4 Risks Associated With Participation in the Clinical Investigation

In addition to device related risks, participants will receive a cystoscopy at visits one and four. Cystoscopy is a commonly performed urological procedure. Adverse effects can include infection, bleeding and pain associated with the cystoscopy.

Some of the possible side effects of anesthetic medication in the urethra include allergic reactions which may include coughing, difficulty swallowing, rash, hives, or swelling. Other possible side effects include high or low blood pressure, stomach upset, tingling sensations in the skin, dizziness, decreased heart rate, and death.

Having blood samples taken from a vein may cause temporary pain or bruising. It is possible for the skin at the puncture site or the vein to become irritated and inflamed. On rare occasions, blood clot formation, bleeding at the puncture site, or infection could occur.

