8.4 Adverse Events

Any Adverse Events (AEs), Serious Adverse Events (SAEs) and Unanticipated Adverse Device Effects (UADEs), to be documented from time of enrollment until the last study visit.

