11.4 Point of Enrollment

Each study candidate to be evaluated during screening will be asked to sign an Informed Consent Form (ICF) prior to the conduct of study specific procedures. The ICF outlines the study procedures, investigational nature of the study, protocol responsibilities, and the expected risks vs. benefits of participation.

Screening is planned to be conducted entirely at Visit 1. Subjects who meet the inclusion and exclusion criteria are enrolled in the study. Device insertion is also planned to be conducted at Visit 1.

The Investigator will retain a Screening Log of those who are considered candidates for enrollment. If a subject later declines or is excluded from enrollment, the Investigator will note the reason for non-participation in the log. Potential subjects will be identified in the log by their initials only.

Figure 9. Flowchart of Subject Screening, Enrollment and Spanner Insertion

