12.1.1 Visit 1: Screening, End of Catheter Use and Stent #1 Placement

- Obtain informed consent.
- Obtain the medical history and perform a physical examination including a digital rectal examination.
- Confirm that subject is not taking anticholinergic medication to manage bladder spasm (an exclusion criterion).
- To obtain a urine specimen:
- Remove the catheter
- Allow the subject to naturally fill his bladder
- Obtain and send a urine specimen for UA & UC&S if indicated.
- Confirm that the UA is negative.
- Perform cystoscopy and take two cystoscopy photographs: (a) of the bulbar urethra looking at a closed external sphincter, and (b) at the verumontanum looking towards the bladder.
- Subjects who meet the inclusion and exclusion criteria will be enrolled into the study.
- For directions for Spanner size selection and insertion refer to *The Spanner Physician Instructions for Use* (see **Attachment A**). Use the Surveyor urethral measurement device to determine the appropriate size Spanner.
- Insert the Spanner.
- Place cystoscope into bulbar urethra and confirm the proper location of the distal anchor. If the Spanner was incorrectly sized, the stent can be removed and replaced with the proper size. Replacement may occur one time only.
- Record any Adverse Event that occurred during sizing and Spanner insertion.
- Allow the subject to drink fluids and wait for a full bladder. Alternatively, investigator may choose to fill the bladder using cystoscopy (if cystoscopy filling is performed, note in the source and the eCRF system).
- With Stent #1 in place, perform the uroflow test followed by measurement of the PVR (abdominal ultrasound). Refer to **Attachment B** for requirements for uroflow testing.
- Provide *Subject Information Booklet for The Spanner* (see **Attachment D**) to the subject. Review each potential Adverse Event with the subject and the appropriate actions to be taken by the subject if they occur.
- Provide *Subject Emergency Removal Card* (see Attachment D) to the subject. Instruct the patient to provide the card to other care providers to inform them that the patient is wearing the Spanner.
- Obtain and send blood sample for serum creatinine.
- Have the subject complete the subject satisfaction questionnaire.
- Interview the subject for signs and symptoms of Adverse Events.
- Place test reports in the subject's study file and record in eCRF..
- Schedule the subject to return for Visit 2 (in 25-35 days).

CONFIDENTIAL

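### Adverse event collection opens at enrolment, after the study cystoscopy at Visit 1, so men who have the cystoscopy and are not enrolled fall outside it

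*Protocol*

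**What the plan says.** **Window.** Protocol 14.8: "All adverse events (AEs) will be observed for each subject from enrollment until termination from the study". Protocol 8.4 says that events are "to be documented from time of enrollment until the last study visit".

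**Enrolment is later than consent.** Under 11.4 each candidate "will be asked to sign an Informed Consent Form (ICF) prior to the conduct of study specific procedures". Enrolment follows when eligibility is established: "Subjects who meet the inclusion and exclusion criteria are enrolled in the study".

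**Order of steps at Visit 1.** In 12.1.1 the step "Perform cystoscopy and take two cystoscopy photographs" is listed immediately before "Subjects who meet the inclusion and exclusion criteria will be enrolled into the study". Table 5 likewise puts the cystoscopy row above the enrolment row.

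**Status of the cystoscopy.** Section 7.4 treats it as a risk of taking part, separate from the device risks: "participants will receive a cystoscopy at visits one and four", and "Adverse effects can include infection, bleeding and pain associated with the cystoscopy". Section 21.1.3 lists complications of cystoscopy and anaesthesia among the anticipated adverse events.

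**Analysis set.** Both the protocol (14.6.1) and the SAP (section 7) restrict the safety population to enrolled subjects.

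**The concern.** The protocol requires an invasive procedure, names its harms, classes them as adverse events, and then opens collection of adverse events only after that procedure is listed as done. Taken literally, an infection, bleed or painful reaction that starts at the screening cystoscopy is outside the window. A man who has the cystoscopy and is found ineligible is also outside the population in which safety is reported.

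What is at stake is a complete record of the harm caused by taking part, and consistent recording across up to 10 centers. A site that follows 8.4 and 14.8 would leave out an event that another site, relying on the interview at the end of Visit 1, would record.

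**Working it through.** The plan states no figure on this point, so the check is a comparison of sections.

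1. **Sequence at Visit 1 (12.1.1):** consent; history and examination; catheter removal and bladder filling; urine specimen; confirmation of a negative urinalysis; cystoscopy; enrolment; sizing with the Surveyor; stent insertion; a second cystoscope placement to check the anchor; voiding tests; general adverse event interview.
2. **Window (8.4, 14.8):** starts at enrolment. The interval from cystoscopy to enrolment is therefore outside it.
3. **Recording steps at Visit 1 (12.1.1):** one covers events during sizing and insertion only. The other is the general interview at the end of the visit, which is reached only by men who went on past enrolment.

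This gives three groups:

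| Group | In the stated window? | In the safety population? |
|---|---|---|
| Had cystoscopy, not enrolled | No | No |
| Enrolled, event starts between cystoscopy and enrolment | No, though the interview may record it | Yes |
| Enrolled, event starts after enrolment (a later infection, the anchor check, the Visit 4 cystoscopy) | Yes | Yes |

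**Can the first group exist?** Several exclusions in 11.2 could plausibly be seen at cystoscopy, such as urethral stricture, bladder stones and intravesical median lobe enlargement. That is my inference; the protocol does not say which criteria the cystoscopy serves. SAP section 9 provides for screen failures in Listing 1, but only with the reason for failure.

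**How large might it be?** The documents give no rate of screen failure. Let s be an assumed share of men having the cystoscopy who are then not enrolled. With 105 enrolled, the number not enrolled is 105/(1 − s) − 105:

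- s = 10%: 105/0.90 − 105 = 11.7, about 12 men
- s = 20%: 105/0.80 − 105 = 26.25, about 26 men
- s = 30%: 105/0.70 − 105 = 45 men

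These are men exposed to the procedure, not adverse events. The documents give no cystoscopy complication rate, so the number of events lost cannot be estimated.

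**Treatment-emergent rule.** Section 14.8 works by date: an event starting on or after the procedure date qualifies. With screening and insertion planned for the same visit (11.4), a cystoscopy event before insertion counts as treatment emergent once it is recorded. Any widening of the window has to deal with this.

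**The case against.** **For enrolled men the loss is mostly on paper.** Table 5 ticks adverse events for Visit 1 as a whole, the visit closes with a general interview, section 26.8 has the investigator record every event, and the date-based rule keeps same-day events once recorded. This stands. A reader might infer that events at the first cystoscopy are lost for all enrolled men, and the documents do not support that. What remains is a contradiction between those instructions and the window, affecting events that start between cystoscopy and enrolment. The gap widens if screening and insertion fall on different days. That is possible because a single visit is only planned, and 11.4.1 allows rescreening.

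**The SAP table is not shown to be wrong.** A reader might infer that the table of events related to the study device or study procedure (SAP 14.2) would omit cystoscopy harm that it was meant to show. The documents do not support this. The SAP appears to use study procedure for the implant: section 8 counts study days from it, section 9 lists it after enrolment, and 14.1.2 does not count events known to have ended before it. Protocol 14.6 names the matching variable as events related to implantation.

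**The group not enrolled may be small.** If the listed order is followed, men who fail on urinalysis, history, medication or bleeding at catheter removal are excluded before the cystoscopy, and urethral length is measured after the enrolment step. Mainly anatomical exclusions remain. This is fair, and it is why the percentages above are only illustrative. It does not close the gap: dispositions and reasons for non-participation are logged, but neither record captures adverse events.

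**The end of the window is largely covered.** Table 5, 12.1.5 and 14.8 already carry collection to the phone call or termination. Only the wording of 8.4 needs aligning.

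**Conclusion.** The point holds as a cheap improvement. Under the stated rules, harm from a study-mandated cystoscopy in consented men who are not enrolled need not be collected and has no place in the safety analysis. It would go too far to say that such events could never be recorded; the plan simply does not require it. Their number is unknown. For enrolled men the gap is small, and consists of a contradiction in wording that could lead sites to record differently.

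The conclusion rests on reading the order in 12.1.1 and Table 5 as the order of conduct, and on enrolment meaning what 11.4 says. It depends on no rate or power assumption. The primary endpoint, the sample size and the decision rule are not affected.

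**What to change.** - **Start of window:** reword 8.4 and 14.8 so that adverse events are collected from signed consent, or from the first study-specific procedure.
- **End of window:** align 8.4 with the follow-up phone call already in Table 5.
- **Reporting:** add one listing of events that start before device insertion, covering all consented men, including those not enrolled.
- **Same-day events:** classify each event on the insertion day as before or after insertion, and state that a pre-insertion event goes only in the new listing and is not also counted as treatment emergent. SAP 14.1.1 already plans to obtain the time of onset; the time of insertion would have to be recorded as well.

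The cost is wording in two protocol sections, a clarification of the treatment-emergent rule, slightly more recording at Visit 1 and one extra listing. The device-related tables are otherwise unchanged.
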